APPENDIX VI: CLINICAL STAGING - CARCINOMA OF THE CERVIX UTERI FIGO CLASSIFICATION 1995

PRE-INVASIVE CARCINOMA STAGE 0: Carcinoma in situ, intraepithelial carcinoma.
(Cases of Stage 0 should not be included in any therapeutic statistics)

INVASIVE CARCINOMA STAGE I: Carcinoma strictly confined to the cervix.

STAGE IA: Invasive cancer identified only microscopically. (All gross lesions, even with superficial staging, are Stage IB cancers) Invasion is limited to measured stromal invasion with maximum depth of 5.0 mm and no wider than 7.0 mm.

STAGE IA1: Measured invasion of stroma no greater than 3.0 mm in depth and no wider than 7.0 mm.

STAGE IA2: Measured invasion of stroma greater than 3 mm and no greater than 5 mm and no wider than 7 mm.

STAGE IB: Clinical lesions confined to the cervix or pre-clinical lesions greater than Stage IA.

STAGE IB1: Clinical lesions no greater than 4.0 cm in size.

STAGE IB2: Clinical lesions greater than 4 cm in size.

STAGE II: The carcinoma extends beyond the cervix but has not extended on to the pelvic wall. The carcinoma involves the vagina, but not the lower third.

STAGE IIA: No obvious parametrial involvement.

STAGE IIB: Obvious parametrial involvement.

STAGE III: The carcinoma has extended on to the pelvic wall. On rectal examination, there is no cancer-free space between the tumor and the pelvic wall. The tumor involves the lower third of the vagina. All cases with hydro-nephrosis or non-functioning kidney.

STAGE IIIA: No extension on to the pelvic wall.

STAGE IIIB: Extension on to the pelvic wall and/or hydro-nephrosis or non-functioning kidney.

STAGE IV: The carcinoma has extended beyond the true pelvis or has clinically involved the mucosa of the bladder or rectum. A bullous edema as such does not permit a case to be allotted to Stage IV.

STAGE IVA: Spread of the growth to adjacent organs.

STAGE IVB: Spread to distant organs.

Notes on Staging:

Stage IA carcinoma should include minimal microscopically evident stromal invasion as well as small cancerous tumors of measurable size. Stage IA should be subdivided into those lesions with minute foci or invasion visible only microscopically as Stage IA1 and the macroscopically measurable microcarcinomas as Stage IA2 in order to gain further knowledge of the clinical behavior of these lesions. The term IB occult should be omitted.

The diagnosis of both Stage IA1 and IA2 should be based on microscopic examination of removed tissue, preferably a cone, which must include the entire lesion. As noted above, the lower limit of Stage IA2 should be that it can be measured macroscopically (even if dots need to be placed on the slide before measurement) and the upper limit of Stage IA2 is given by measurement of the two largest dimensions in any given section. The depth of invasion should not be more than 5 mm taken from the base of the epithelium, either surface or glandular, from which it originates. The second dimension, the horizontal spread, must not exceed 7 mm. Vascular space involvement, either venous or lymphatic, should not alter the staging but should be specifically recorded as it may affect treatment decisions in the future.

Lesions of greater size should be staged as IB.

As a rule, it is impossible to estimate clinically whether a cancer of the cervix has extended to the corpus. Extension to the corpus should therefore be disregarded.

A patient with a growth fixed to the pelvic wall by a short and indurated, but not nodular, parametrium should be allotted to Stage IIB. It is impossible at clinical examination to decide whether a smooth and indurated parametrium is truly cancerous or only inflammatory. Therefore, the case should be placed in Stage III even if according to the other findings the case should be allotted to Stage I or Stage II.

The presence of the bullous edema as such should not permit a case to be allotted to Stage IV. Ridges and furrows into the bladder wall should be interpreted as signs of submucous involvement of the bladder if they remain fixed to the growth at palpation (i.e., examination from the vagina or the rectum during cystoscopy). A cytological finding of malignant cells in washings from the urinary bladder requires further examination and a biopsy from the wall of the bladder.

The depth of invasion should be no more than 5 mm taken from the base of the epithelium, either surface or glandular, from which it originates. Vascular space involvement, either venous or lymphatic, should not alter the staging.

APPENDIX VII: HDR BRACHYTHERAPY

I. Vaginal Surface Dose – HDR (03/23/2009)

The vaginal mucosa will receive 138-140% of the prescribed dose to Point A—8.28-12.6 Gy. The vaginal mucosa dose is defined on the lateral surface of the ovoids taken through a coronal section. Computerized dosimetry is required for each HDR insertion.

In patients with either significant vaginal narrowing due to tumor infiltration or normal anatomy, tandem and cylinders may be necessary to encompass the volume of disease. Since little or no packing will be possible in these patients, the vaginal mucosa dose should not exceed 110-120% of the prescribed dose to Point A, unless the bladder and rectum are receiving doses within normal tissue tolerance.

II. Normal Tissue Tolerance

In LDR brachytherapy, most institutions attempt to keep the total bladder dose below 75 Gy and the total rectal dose below 70 Gy, unless the tumor is poorly regressing and/or observing these normal tissue tolerances would compromise tumoricidal radiation doses. The total bladder and rectal dose will be less in HDR brachytherapy because of the dose rate effect. There are a number of methods available to calculate these normal tissue doses. The linear quadratic model (LQM), total rectal and bladder dose, in addition to the ratio of bladder or rectal dose divided by the Point A dose, have been employed to calculate normal tissue tolerance. Certainly, if the total bladder and/or rectal dose equals or exceeds the above LDR guidelines, or if the ratio of the normal tissue dose to the Point A dose is 80% or greater, then the packing will need to be re-evaluated. The LQM is probably the most accurate model at present to evaluate normal tissue tolerance to account for the dose rate effect. Using the LQM, a dose to the late responding tissues of 70 Gy corresponds to a Gy3 of 120 (Gy3-not real dose, but biologically effective one to the late responding tissues). A total dose of 75 Gy corresponds to a Gy3 of 130. These Gy3 terms are helpful in calculating the total doses to the normal tissues when adjusting for the dose rate effect.

In order to stay below an LDR equivalent of 70 Gy to the rectum (120 Gy3) for five HDR insertions, including the 45 Gy contributions from the external beam radiation, the rectum should receive less than 4.1-6.1 Gy for each HDR fraction of 6-9 Gy (68% of the prescribed dose to Point A). The dose to the bladder should be less than 4.6-6.9 Gy per HDR fraction of 6-9 Gy (77% of the prescribed dose to Point A). As in LDR brachytherapy, every attempt should be made to deliver tumoricidal doses, even if the late responding tissues receive a slightly higher dose. (03/23/2009)

III. Packing

[figure not shown]
For both LDR and HDR brachytherapy, careful attention should be paid to the bladder and rectal packing. Radio-opaque gauze is recommended to determine the location of the packing for calculation of ICRU #38 bladder and rectal doses. Using the posterior blade of a speculum may facilitate rectal packing. Bladder and rectal points will be taken for normal

tissue tolerance for both HDR and LDR brachytherapy according to ICRU recommendations (ICRU #38) as well as standard institutional bladder and rectal points. These ICRU #38 and institutional bladder and rectal dose points must be calculated but dose modifications should not be made solely based upon these calculations (Refer to [Appendix IX](#)).

IV. Imaging - HDR

A dedicated brachytherapy suite in which an orthogonal x-ray pair can be taken is the ideal setting for the HDR insertions. This will allow for patient immobilization and a reduction in the overall time spent with applicators in the gynecologic tract. If patients must be moved to another room for an orthogonal x-ray pair, every attempt should be made to maintain rigid immobilization. Since the HDR tandem diameter is only 2.5 mm, as opposed to a LDR tandem diameter of 5.0 mm, sounding the uterus is often easier with a potential increased risk for uterine perforations. If a uterine perforation is suspected, it is highly recommended that a transabdominal ultrasound be performed to rule out this event. Ultrasound may also facilitate uterine sounding with difficult insertions.

APPENDIX VIII: DESCRIPTION OF POINTS A AND B AND ICRU BLADDER/RECTAL DOSE REPORTING POINTS

[figure not shown]

RPC 02/92

Point A is defined as 2 cm along the intrauterine tandem in the superior direction from the flange, and 2 cm perpendicular to the tandem in the lateral direction.

Point B is defined as 2 cm along the intrauterine tandem in the superior direction from the flange, and 5 cm lateral from the midline of the patient.

Description of ICRU 38 Bladder/Rectal Dose Reporting Points

[figure not shown]

The bladder reference point is obtained as follows. A Foley catheter is used. The balloon must be filled with 7 cm^3 of radio-opaque fluid. The catheter is pulled downwards to bring the balloon against the urethra. On the lateral radiograph, the reference point is obtained on an anterio-

[figure not shown]
posterior line drawn through the center of the balloon. The reference point is taken on this line at the posterior surface of the balloon. The frontal radiograph, the reference point is taken at the center of the balloon.

The point of reference for the rectal dose is obtained as follows. On the lateral radiograph, an anteroposterior line is drawn from the lower end of the intrauterine source (or from the middle of the intravaginal sources). The point is located on this line 5 mm behind the posterior vaginal wall. The posterior vaginal wall is visualized, depending upon the technique, by means of an intravaginal mould or by opacification of the vaginal cavity with a radio-opaque gauze used for the packing. On the AP radiograph, this reference point is at the lower end of the intrauterine source or at the middle of the intravaginal source(s).

APPENDIX IX: BLANK DIAGRAM ANTERIOR

APPENDIX X: BLANK DIAGRAM LATERAL

APPENDIX XI: COLLECTION AND SHIPPING INSTRUCTIONS FOR SERUM AND CERVICAL AND ANAL SWABS FOR EXPLORATORY OBJECTIVE SPECIMENS

SPECIMEN COLLECTION

The specimen collection requirements for exploratory objective specimens are detailed in the AMC-081 Manual of Procedures.

SAMPLE SHIPPING AND LABELING

Specimens should be batched at each site, and shipped via World Courier, every six months to the study laboratory. The shipping and labeling requirements are detailed in the AMC-081 Manual of Procedures.

RECORD OF SPECIMENS

This study will track specimens via GlobalTraceSM, a component of the AMC AdvantageEDCSM system. The GlobalTraceSM shipment manifest must accompany all specimen shipments.

HPV DNA TESTING

To perform HPV DNA testing on cervical and anal swab specimens, the swabs will be obtained following the procedures listed in the AMC-081 MOP and inserted into Specimen Transport medium (STM). The swab should then be cut with sterile or single-use scissors to allow the swab to fit in the vial. The cap should then be replaced securely and sealed with tape or parafilm. The specimens must then be stored at -20°C or -80°C prior to shipping every 6 months. The specimens should be shipped Monday through Wednesday on dry ice to:

[name]
University of California, San Francisco
[name]
San Francisco, CA 94143-0654
[contact]

Laboratory methods: A crude DNA preparation is made from the STM/swab specimen. First the specimen is incubated at 56°C for 1 hour, then proteinase K (Invitrogen Life Technologies) is added to a concentration of 250 µg/ml and incubated at 50°C overnight. In the morning the proteinase K is heat inactivated, and 200 µl of the specimen is ethanol precipitated and suspended in 25 µl Tris-EDTA buffer. Five µl of sample are used for PCR amplification. PCR products from positive samples were also typed by dot-blot hybridization using 38 individual type-specific probes as well as 2 separate mixtures of types.

The presence or absence of HPV and beta-globin DNA is determined using DNA hybridization. Negative controls for each blot consist of amplification of DNA of BJAB cells and tubes

containing all reaction components except target DNA. Positive controls consist of amplification of DNA from 100 SiHa cells as well as amplified DNA from the individual HPV types being sought. Five percent of the samples are amplified in duplicate. Six μ L of the PCR amplification mixtures are applied to dot blots and the DNA is fixed on the membrane. To detect HPV DNA, the membranes are pretreated in 0.1 x sodium chloride-sodium phosphate-EDTA (SSPE), 0.5% sodium dodecyl sulfate for 30 min at 65°C. Probes consisting of amplified biotinylated DNA from HPV 16, HPV 18, HPV 11 and HPV 51 are denatured and added in the presence of 2 mg/mL sheared salmon sperm DNA to the hybridization buffer and hybridized at 55°C for at least 1.5 h. After washing, streptavidin-horse radish peroxidase (SA-HRP) (Vector Laboratories, Burlingame, CA) is added to the blots at a concentration of 30 ng/mL in 250 mL of wash solution and binding allowed to occur with gentle agitation for 15 min at room temperature. After vigorous washing, detection of HPV types is performed using Enhanced ChemiLuminescent detection (ECL) (Amersham, Arlington Heights, IL) according to the manufacturer's instructions. Type-specific probing is performed using biotinylated oligonucleotide probes at a final concentration of 0.5 pmol/mL for the following HPV types individually: 6/11, 16, 18, 26/69, 30, 31, 32/42, 33, 34, 35, 39, 45, 51, 52, 53, 54, 56, 57/2/27, 58, 59, 61, 62, 66, 67, 68, 70, 71, 72, 73, 81, 82, 83, 84, 85, 86/87, 90/106, 97, 102/89, as well as 2 separate mixtures. Mix1 contains 7, 13, 40, 43, 44, 55, 74, and 91, and Mix2 contains 3, 10, 28, 29, 77, 78, and 94. A sample is considered HPV positive when it was positive with the consensus probes. Specimens positive with the consensus probes but negative with the individual type probes are considered to have one or more "other" types. Specimens negative for beta-globin gene amplification are excluded from analysis.

DNA Methylation Analysis

DNA from swab material will be used to allow us to determine in a descriptive way if the methylation patterns are different and might provide some clues regarding the role of HPV methylation in progression to cancer. DNA will be treated with sodium bisulfite using the EZ DNA Methylation Kit (Zymo Research, Orange, CA) in preparation for MSP. The methylation-specific PCR reactions will utilize 10 ng of the sodium bisulfite-treated DNA in 12.5 μ L of 2x Brilliant SYBR Green QPCR Master Mix (dNTPs, Taq DNA polymerase, 2.5 mM MgCl₂) (Stratagene), 30 nM ROX reference dye, and 500 nM of forward and reverse primers, in a final volume of 25 μ L. Real-time methylation-specific PCR will be performed on a Mx3000 Thermocycler (Stratagene, La Jolla, CA). The methylation-specific primer sequences are listed in [Table X](#). The real time methylation-specific PCR reaction utilizes the following conditions: Segment one - one cycle - 95°C for 10 minutes; Segment two - 65 cycles - 95°C for 30s, then 60°C-64°C (depending on primers) for 30s, then 72°C for 30s; Segment three - one cycle - 72°C for 30s, then 95°C for 1 minute, then 55°C for 30s. Normal male white blood cell genomic DNA (Novagen, Madison, WI) will be used as a negative DNA control and CpGenome Universal Methylated DNA, Human Male (Chemicon International, Temecula, CA) will be used as a positive control. Unmethylated MyoD primer sets will be used to confirm the presence of PCR-amplifiable DNA in each sample. Each gene will be scored as positive or negative for methylation; the assay will not be quantitative. The individual target gene will be considered positive for methylation if there is a PCR product detected at the appropriate temperature of the dissociation curve, and the gene will be considered negative if there is no peak at the appropriate

temperature of the dissociation curve. Samples will be considered non-informative if there is no PCR product generated from the gene of interest and the unmethylated MyoD control.

Table X. Real-Time Methylation Specific PCR Primers and Probes

Locus	5' to 3' Forward Primer	5' to 3' Reverse Primer
MYOD1	CCAACTCCAAATCCCCTCTCTAT	TGATTAATTAGATTGGGTTAGAGAAGGA
APC	TTATATGTCGGTTACGTGCGTTATAT	GAACCAAAACGCTCCCCAT
hMLH1	CTATGCCGCCTCATCGT	CGTTATATATCGTCGTAGTATTCTGT
MGMT	GCGTTTCGACGTTCGTAGGT	CACTCTCCGAAAACGAAACG
GSTP1	AGTTGCGCGGCGATTTC	GCCCCAATACTAAATCACGACG
p16^{INK4a}	TTATTAGAGGGTGGGGCGGATCGC	GACCCCGAACCGCGACCGTAA
CDH1	AATTTAGGTTAGAGGGTTATCGCGT	TCCCCAAAACGAAACTAACGAC
RARβ	AAGTAGTAGGAAGTGAGTTGTTAGA	CCAAATTCTCCTTCAAATAA
HIC1	GTTAGGCGGTTAGGGCGTC	CCGAACGCCCTCATCGTAT
TSLC1	GTGAGTGACGAAATTGTAATGTTGGTT	AATCTAACTTCTTACACCTTATTAAAA
RASSF1A	GCGTTGAAGTCGGGGTTC	CCCGTACTCGCTAACCTTAAACG
DAPK	GGATAGTCGGATCGAGTTAACGTC	CCCTCCCAAACGCCGA
FHIT	TTGGGGCGCGGGTTGGGTTTACGC	CGTAAACGACGCCGACCCACTA
PTEN	GGTTTTCGAGGCCTCG	CGCCTCACAAACGACTCAACT
p14^{ARF}	GTGTTAAAGGGCGGCGTAGC	AAAACCCCTCACTCGCGACGA
VHL	TGGAGGATTGCGTACGC	GAACCGAACGCCGCGAA
p73	GGACGTAGCGAAATCGGGTTTC	ACCCCGAACATCGACGTCCG
FANCF	TTTTGCGTTGGAGAACGTTTC	ATACACCGCAAACCGCCGACGAACAAACG
BRCA1	TCGTGGTAACGGAAAAGCGC	AAATCTCAACGAACTCACGCCG
TNFRSF10C	TTACCGTACGAATTAGTTAAC	ATCAACGACCGACCGAAACG
TNFRSF10D	GGGATAAAGCGTTCGATC	CGACAAACAAAACCGCG

SERUM SPECIMENS

HPV Serology

Serology to measure neutralizing antibodies against HPV 16 and HPV 18 will be performed using a pseudovirion (PsV)-based neutralizing assay (PBNA). HPV-16 and HPV-18 PsVs were

prepared as described. PsVs will be synthesized using the 293TT cell line transfected with the p16sheLL, p18sheLL and pYSEAP plasmids. PsVs will be purified by loading on a 2% agarose gel column. The crude stock and column-purified stock will be titrated using 293TT cells. Neutralization assays will be performed using established methods. PsVs carrying the SEAP-encoding plasmid will be incubated with participants' sera for 1 hour on ice. The mix will be added to the 293TT cells and SEAP activity will be measured in the medium after 72 hours. SEAP in 25 μ l of culture supernatant will be detected using the Great Escape SEAP 2.0 detection kit (Clontech, Mountain View, CA) per the manufacturer's instructions. Chemiluminescence will be read on a microplate reader (Dynatech Laboratories, Chantilly, VA). Negative controls consist of sera known to lack neutralizing HPV antibodies. Positive controls consist of assays performed with addition of heparin (1mg/ml) and sera known to contain neutralizing antibodies from HPV-16- and HPV-18-vaccinated individuals. The neutralization titer will be defined as the reciprocal of the highest dilution of test serum that reduce the SEAP activity by at least 50% in comparison with the reactivity in the wells that receive PsV but no antibody. All assays will be done in duplicate at four different dilutions-1:100, 1:200, 1:400 and 1:800. Data for each serum sample at each dilution represent an average of the duplicate wells. Samples that do not reduce SEAP activity by 50% or more at a 1:100 dilution will be considered to be seronegative for analysis. In some cases where the titers are higher than 800 the assays will be repeated with higher dilutions to obtain accurate titers.

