To determine the HPV DNA types and HPV strain variants present in cervical cancer and in the anus of cervical cancer patients, frequency tables of HPV DNA types and HPV strain variants will be constructed for cervical and anal samples at baseline, end of treatment and at recurrence (if applicable). The binomial proportion and its 95% confidence interval will be used to estimate the proportion of each HPV DNA type and each HPV strain variant that occurs in at least 5% of patients in cervical or anal specimens. Concordance between anal and cervical specimens with respect to detection of specific HPV DNA types and HPV strain variants will be assessed using McNemar's chi-square test.

Changes in HPV DNA types and strain variants between baseline and post-treatment measurements will be assessed using McNemar's chi-square test for each DNA type and

strain variant. Proportional hazards models and logistic regression models will be used to evaluate the association of change in DNA types with progression free survival and local control, respectively.

The binomial proportion and its 95% confidence interval will be used to estimate the proportion of patients who have abnormally methylated genes for each gene tested.

Gene methylation profiles will be summarized at baseline.

Concordance between gene methylation profiles between cervical and anal swabs will be assessed at baseline using the kappa statistic.

The chi-square test will be used to assess the association between baseline gene methylation profiles and cervical persistence or recurrence.

The logistic regression model will be used to assess the effects of HPV-16 and HPV-18 serologic titer levels with disease persistence or recurrence using the logarithmic transformation for the titer levels. Similarly, the effects of changes in HPV-16 and HPV-18 titer levels from baseline to treatment on outcome measures (progression free survival, local control) will be assessed using proportional hazards models and logistic regression models.

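### As printed in Table X, the RARβ primers contain no CpG site, so they are not methylation-specific and a RARβ call would not be valid until the sequences are checked

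*Combined protocol and SAP*

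**What the plan says.** Appendix XI, under DNA Methylation Analysis, treats swab DNA with sodium bisulfite and runs a real-time PCR with SYBR Green detection. It introduces Table X with the words "The methylation-specific primer sequences are listed in" and makes no exception for any target gene. The MyoD set has a separate role: "Unmethylated MyoD primer sets will be used to confirm the presence of PCR-amplifiable DNA in each sample".

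Scoring is binary. A target gene is "considered positive for methylation if there is a PCR product detected at the appropriate temperature of the dissociation curve", and negative if there is no peak there. A sample is non-informative only when neither the target gene nor the MyoD control gives a product. Normal white-cell DNA is the negative control and universally methylated DNA the positive control. Nothing is said about a locus that amplifies in the negative control.

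Table X gives the RARβ forward primer as "AAGTAGTAGGAAGTGAGTTGTTAGA" and the reverse as "CCAAATTCTCCTTCAAATAA". Its title mentions probes, but no probe sequence is listed.

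Section 11.1 plans to "estimate the proportion of patients who have abnormally methylated genes for each gene tested". It also compares methylation profiles between cervical and anal swabs by kappa, and tests baseline profiles against persistence or recurrence by chi-square. Section 1.2.2 names RARβ among the genes of interest.

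**The concern.** Bisulfite treatment converts unmethylated cytosine and leaves methylated cytosine in place. Section 1.2.2 places the methylated cytosines in regions rich in CpG dinucleotides. After treatment, methylated and unmethylated copies of a locus therefore differ only at those sites. A primer can favour the methylated copy only if it lies over at least one CpG and is written with CG there. A pair with no CG cannot do this.

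If the printed RARβ sequences are the ones used, a product does not show methylation, yet the scoring rule would record it as such. That call would enter the RARβ proportion in section 11.1 and contribute to the profiles used for the kappa and chi-square analyses.

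**Working it through.** The documents state no figure on this point, so there is none to reproduce. The check is a count.

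**Inputs.** Both primers of all 21 loci in Table X: MYOD1 and 20 targets. The CpG dinucleotide reads CG on either strand, so the count is the number of CG pairs in each primer as printed.

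| Locus | Forward | Reverse | Total |
|---|---|---|---|
| MYOD1 (control) | 0 | 0 | 0 |
| **RARβ** | **0** | **0** | **0** |
| TSLC1 | 1 | 0 | 1 |
| APC | 3 | 1 | 4 |
| CDH1 | 2 | 2 | 4 |
| PTEN | 2 | 2 | 4 |
| hMLH1 | 2 | 3 | 5 |
| GSTP1 | 3 | 2 | 5 |
| HIC1 | 2 | 3 | 5 |
| RASSF1A | 2 | 3 | 5 |
| DAPK | 3 | 2 | 5 |
| p14 | 2 | 3 | 5 |
| TNFRSF10D | 2 | 3 | 5 |
| p16 | 2 | 4 | 6 |
| VHL | 2 | 4 | 6 |
| BRCA1 | 3 | 3 | 6 |
| TNFRSF10C | 2 | 4 | 6 |
| MGMT | 4 | 3 | 7 |
| FHIT | 3 | 4 | 7 |
| p73 | 3 | 4 | 7 |
| FANCF | 2 | 5 | 7 |

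**Result.** Eighteen targets have at least one CpG in each primer and 4 to 7 per pair. TSLC1 has one in 27 + 27 = 54 bases. RARβ has none in 25 + 20 = 45 bases.

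**Base composition.** The RARβ forward primer has 0 C and 9 G; the reverse has 6 C and 0 G. The control pair, "CCAACTCCAAATCCCCTCTCTAT" and "TGATTAATTAGATTGGGTTAGAGAAGGA", has 11 C and 0 G, then 0 C and 9 G. In both pairs one primer lacks C and the other lacks G, so no CG can occur.

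**What a RARβ product would then mean.** Three results are possible.

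- *The primers lie over no CpG.* They amplify regardless of methylation, and a product shows only that DNA was present.
- *The primers lie over CpGs in their converted, unmethylated form.* The forward primer contains TG twice and the reverse CA twice, which is how such sites would read. The pair would then favour unmethylated DNA, and the call would be reversed. The genomic sequence is not given, so this cannot be settled.
- *The primers anneal poorly.* Nearest-neighbour melting estimates at the stated 500 nM primer concentration, with monovalent salt assumed to be 50 to 240 mM, are 53.5–61.6 °C forward and 46.2–53.9 °C reverse. The stated annealing range is 60–64 °C. A weak or absent product would be scored negative whenever MyoD amplifies. This is only suggestive: the TNFRSF10C forward primer also falls below the range (48.5–56.1 °C), although it carries CpGs.

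**The case against.** The strongest defence is that scoring depends on more than priming. A positive call needs a product at the appropriate dissociation temperature. If CpGs lie between the RARβ primers, methylated and unmethylated products could melt at different temperatures, and the curve could separate them. This stands as a possibility. However, Appendix XI gives no amplicon, no RARβ melting temperature and no statement that this locus is scored differently, and SYBR Green detection with no listed probe adds no sequence specificity.

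Second, the negative control might expose a pair that ignores methylation. That is fair, but no action is specified if it does.

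Third, the table may be misprinted or misread from the PDF. Other rows also look imperfect for converted sequence: the hMLH1 reverse primer has a C outside any CpG, and the PTEN forward primer has two. Character errors cannot be excluded, so the first step must be verification.

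A reader might infer that RARβ would be scored methylated in nearly every amplifiable swab, giving a false 100% prevalence and undefined test statistics. The documents do not support that. It is one of the three possibilities above. In that branch alone the exact lower 95% limit would be 0.025^(1/38) = 0.907 for 38 women, or 0.025^(1/45) = 0.921 for all 45. The larger number is the natural ceiling, because baseline swabs precede treatment (section 5.1.2) and 38 is the evaluable number for treatment completion (section 11.2). Only the proportion is stated per gene. Kappa and chi-square are planned on profiles, so one constant locus would make only a RARβ-specific version undefined. A positive added equally to every profile would not by itself create an association with recurrence.

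**Conclusion.** The point holds as an inconsistency between the printed RARβ sequences and the methylation-specific label. As written, the pair cannot select methylated template at priming, and a positive score from it is not a valid methylation call. The size and direction of the resulting error cannot be determined. TSLC1 is a lesser matter: one CpG in one primer may give some selectivity, so it warrants a check but is not shown to fail.

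This rests on the sequences being as printed, on standard bisulfite chemistry, and on the absence of a validated melting rule for RARβ. The importance is minor. One of 20 loci in an exploratory, descriptive objective is affected; the treatment-completion outcome, the sample size and the safety assessment do not depend on it.

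**What to change.** Before any swab is assayed:

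1. Check both RARβ primers and the TSLC1 reverse primer against the laboratory's primer list. If Table X is misprinted, correct it.
2. If the RARβ sequences are confirmed, replace them with primers that contain CpG sites, or drop RARβ from the panel. The exception is a validated dissociation-temperature rule for this locus; in that case state the rule in Appendix XI.
3. Add one line to Appendix XI: a locus that gives a scored-positive product in the normal white-cell negative control is excluded from the methylation analyses in section 11.1.

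The cost is a sequence check, possibly new primers, and a short text change. No extra specimens are needed. The downside is possibly one fewer gene.
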